This will be a prospective, randomized-controlled study in which qualified patients with partial edentulism will be treated with at least two dental implants. Implant sites will be randomly assigned to receive either a test (T3 Nanotite Certain Tapered Prevail - BNPT) or control (Nanotite Certain Tapered - NINTxx) implant (80:20 – test – control randomization ratio). All implants will be placed in a single-stage manner using torque-indicating instruments to document the torque-insertion profile. At implant placement surgery test implants will receive Encode healing abutments whereas control implants will be provisioned with prefabricated or standard abutments. For the test group an Encode Level Impression will take place at 10 weeks and individual final abutments and prosthesis placement at 3 months following implant placement surgery. A fixture level impression will be taken for control implants at week 10, followed by final restorations at month 3. All implants will be allowed to integrate without occluding forces and all restorations will be cemented. Resonance frequency assessment procedures will be done at implant placement surgery and at prosthesis insertion. Cumulative success rate and crestal bone regression will be the primary study endpoint. Enrollment will continue until 100 patients have completed final prosthetic treatment at the participating study centers. Additional control cases will be derived from on-going clinical trials of the NINT implants matched with the prospective study control group for baseline variables, restorative type (STR, fixed bridges), and implant dimensions. The additional control cases will bring the test and control groups to a 1:1 ratio and allow for more powerful analyses.

Study (null) hypothesis:

The functional success (survival and success rate) of the T3 implant to maintain integration and support of prostheses in this study will be no different than of the control implant. Moreover there crestal bone changes that take place after placement and loading of the T3 Certain Tapered Prevail (BNPTxxx – test implant) and Certain Tapered (NINTxx - control implant) will be the same.

[figure not shown]
MATERIALS AND METHODS

Implants with similar geometry but with different surface roughness will be evaluated. All implants are titanium root-form dental implants. The test implant has an integrated platform switch feature, whereas the restorative components of the control implant will be matched.

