- Probably related - an event that follows a known or suspected response pattern, is confirmed by improvement upon stopping or reducing treatment, and cannot be reasonably explained by the known characteristics of the patient's clinical state.
- Definitely related - an event that follows a known or suspected response pattern, is confirmed by improvement upon stopping or reducing treatment, and reappears upon repeated exposure.
- Unknown - relationships for which insufficient information exists.

Failure to use an implant due to improper placement is not an adverse event in the absence of pathology, but is censored data for the survival analysis and must be reported on the Implant Failure Form (ICF).

Medical Adverse Events

Death, serious illness or major trauma, whether implant success is affected or not, is an adverse event and must be reported on the Medical Event form (AME). A medical adverse event will be assessed based on causality (criteria described in dental adverse event section) and severity. Severity criteria are described as follows:

- Mild - the adverse reaction does not interfere in a significant manner with the patient's normal functioning level.
- Moderate - the adverse reaction produces some impairment of functioning but is not hazardous to health; may be uncomfortable.

- Severe - the adverse reaction produces significant impairment of functioning or incapacitation and is a definite hazard to the patient's health; this can lead to 1) death or decreased life expectancy, 2) an immediate life-threatening event, 3) inability to resume usual life pattern, 4) significant disability or incapacity.

STATISTICAL ANALYSES

The primary efficacy parameter will be the duration of implant survival (failure-free utilization or lack of mobility) from implant placement. The fraction of surviving implants and cases at the completion of 1, 2 and 5 years of function will be evaluated. Implant survival differences of >5 % will be considered clinically relevant. Clinical outcomes will be evaluated by clinical signs and symptoms of implant failure and dental and medical events.

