Secondary efficacy parameters will be prosthesis survival and procedural success. For each patient, survival time after study surgery will be calculated by the duration of failure-free, intervention-free, duration of support of a prosthesis. Implant survival curves will be estimated for the Test and Control treatment group and these will be compared using the Log Rank or Wilcoxon tests. Survival rates at six months (Study Visit 6), one-year (Study Visit 7) and 5 years (visit 11) will be computed for each treatment group, and compared using chi-square. The sample size determinations were based upon survival to the five-year point as a measure of efficacy.

A secondary outcome question of this study is the equivalence in the changes in alveolar crestal bone between the modified implant (T3) and its predecessor the Certain™ implant. In previous studies of Biomet3i implants (Calvo-Guirado 2011, Zetterqvist 2009; Östman et al. 2010), crestal bone change-from-baseline values have ranged from a mean of 0.37 mm to 1.2 mm at the six month (Visit 6) time point. For purposes of this study there will be an assumption that the control implant will have a change-from-baseline mean value of 0.75 mm at the 6 month (Visit 6) time period. To declare equivalence the Test implant system will need to have a crestal bone change-from-baseline mean bone level regression of 0.75 ± 0.15 mm; or to declare superiority a mean value of 0.55 mm or lower. For the functional evaluation of crestal bone regression will be determined for each of the treatment groups at 3 months (Visit 5), six months (Visit 6) and at each of the annual study visits. The significance of these changes from baseline will be evaluated at each time point using a paired t-test or a Wilcoxon signed rank test. At each time point the treatment groups will be compared using the analysis of variance or the blocked Wilcoxon test, as appropriate. Analysis to determine association with other variables will use “exact” rather than “asymptomatic” methods where necessary.

The Test and the Control implants will be considered the experimental units. The influence of the length and diameter of the implants as a covariate on survival will be determined during the analysis. The comparability of the Test and Control treatment groups will be determined with regard to demographic

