variables (including age, gender) and variables relating to the severity of disease (such as existing dental pathology and dental hygiene). For the continuous variables age and evaluations of oral hygiene and the gingival biotype, the groups will be compared using either analysis of variance or blocked Wilcoxon, as appropriate. For the qualitative variables, sex, smoking habit, existing dentition, concomitant conditions, a chi-square contingency table analysis will be used. Analysis to determine association with other variables will use "exact", rather than asymptotic methods where necessary.

All dental and medical events will be tabulated. Treatment groups will be compared using chi-square with regard to the number of patients in each group who experience those events most frequently and are assessed by the investigator as being probably or definitely related to the investigational treatment. Statistical significance will be declared if the two sided p-value is > 0.05 .

Calvo-Guirado JL, Gómez-Moreno G , López-Marí L, Guardia J, Negri B, Martínez-González JM. Crestal bone loss evaluation in osseotite expanded platform implants: a 5-year study. Clin Oral Impl Res 2011 21 MAR 2011
DOI: 10.1111/j.1600-0501.2010.02130.x

Östman PO, Wennerberg A, Albrektsson T. Immediate occlusal loading of NanoTite Prevail implants: a prospective 1-year clinical and radiographic study. Clin Implant Dent Relat Res. 2010 Mar;12(1):39-47.

Records / Data Retention

Case Report Forms (CRFs) will be prepared by 3i for the collection of data. These forms will be used for the entire duration of the study. The original of the completed CRF will continuously be collected by the study monitor for analysis and storage. Only original radiographs (or digital images saved on a disc) will be accepted and maintained by the study sponsor. Investigators will keep a copy of the CRFs and will maintain these records for at least three years.

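### The primary survival parameter is tested by log-rank or Wilcoxon and by chi-square at three landmarks, and the plan does not say which comparison decides

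*Combined protocol and SAP*

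**What the plan says.** All of this is in the Statistical Analyses section unless stated otherwise.

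- Primary parameter: "The primary efficacy parameter will be the duration of implant survival (failure-free utilization or lack of mobility) from implant placement".
- First landmark list, in the same paragraph: "The fraction of surviving implants and cases at the completion of 1, 2 and 5 years of function will be evaluated". No test is attached.
- Curve comparison, in the next paragraph, which opens with the secondary parameters: implant survival curves are estimated for each arm and "these will be compared using the Log Rank or Wilcoxon tests". There is no rule for choosing between the two.
- Second landmark list: "Survival rates at six months (Study Visit 6), one-year (Study Visit 7) and 5 years (visit 11) will be computed for each treatment group". The arms are then tested against each other at these points by chi-square.
- Sizing: "The sample size determinations were based upon survival to the five-year point as a measure of efficacy". No calculation is shown.
- Significance level: "Statistical significance will be declared if the two sided p-value is > 0.05". The inequality is printed the wrong way round, and the sentence closes the paragraph on dental and medical events. It is the only level in the document.
- The Study (null) hypothesis section states that "The functional success (survival and success rate) of the T3 implant to maintain integration and support of prostheses in this study" will not differ from control. It names neither a test nor a time point.

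**The concern.** The main question has one curve comparison, with an open choice of test, and three landmark comparisons. Nothing ranks them, divides the error rate among them or marks any as supportive. Followed literally, the plan allows several full-level decisions on one endpoint. The results can also disagree: an imbalance at six months may be gone by five years, or appear only then. One reader could cite a significant landmark as a difference, and another a non-significant curve test as no difference, both within the plan.

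Two neighbouring questions are separate and not argued here. One is which endpoint is primary, since the Study Design section names success rate and bone loss instead. The other is whether chi-square suits censored data.

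**Working it through.** **1. The plan's own figure.** The documents state no overall error rate. The sample size (100 patients, at least 200 implants) cannot be reproduced, because no survival rates, power, hazard ratio or dropout are given.

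**2. Inputs.** From the documents: 200 implants, 80:20 allocation and the planned top-up of controls to 1:1. Hence 0.8 × 200 = 160 test v 40 control, or 160 v 160 after the top-up. Landmarks are Months 6, 12 and 60. Inferred: two-sided 0.05. Assumed, because the documents are silent: failure rate, failure timing, dropout and independence of implants.

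**3. Upper bound if the tests were independent.** 1 − 0.95³ = 14.3% for three tests; 1 − 0.95⁴ = 18.5% for four. The tests share failures, so the true rates are lower.

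**4. Large-sample check of the three chi-squares.** With F the cumulative failure proportion and s < t, the null correlation of two landmark statistics is √[F(s)(1−F(t)) / (F(t)(1−F(s)))]. Example: 5% five-year failure, 30% of it by Month 6, and a quarter of the remainder by Month 12. Then F = 0.015, 0.02375 and 0.05, and the correlations are:

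- Months 6 and 12: √(0.015×0.97625 / (0.02375×0.985)) = 0.79
- Months 6 and 60: √(0.015×0.95 / (0.05×0.985)) = 0.54
- Months 12 and 60: √(0.02375×0.95 / (0.05×0.97625)) = 0.68

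The multivariate-normal chance that at least one exceeds the 5% limit is 11.1%. With 10%, 50% or 80% of failures by Month 6 it is 12.5%, 9.7% or 7.8%.

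**5. Simulation under no difference.** Chance of at least one p < 0.05 among log-rank and the three landmark tests:

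| Assumptions | Landmark test | Rate |
|---|---|---|
| 3–20% five-year failure, 30–80% of it by Month 6, 10% dropout, 3,000 runs per setting; 160 v 40 | uncorrected chi-square | 6.1–13.5% |
| same; 160 v 160 | uncorrected chi-square | 6.9–13.2% |
| 5% or 10% failure, 30–80% by Month 6, no dropout, 8,000 runs per setting; both sizes | uncorrected chi-square | 5.3–11.5% |
| same | continuity-corrected | 4.0–7.0% |
| same | Fisher exact | 4.4–7.1% |

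One pre-named log-rank test ran at about 3–6%. In the first two rows the rate falls as failures come earlier: 8–13.5% with 30% by Month 6, 9–11% with 50%, and 6–9% with 80%. Letting the analyst choose Wilcoxon as well adds 0.2 points or less, so the excess comes from the landmarks.

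**6. Sparse counts.** At 5% failure, 40 control implants give 0.05 × 40 = 2 expected failures in five years. One control failure against none (1/40 v 0/160) gives X² = 200×160² / (40×160×1×199) = 4.02, p = 0.045 uncorrected. It gives p = 0.45 with continuity correction and 40/200 = 0.20 exact. At 160 v 160, 2 v 0 gives X² = 2.01, p = 0.16; four failures against none are needed.

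**7. The two lists.** Six months appears only in the tested list, two years only in the other. The tested list is tied to study visits, and the other counts years of function. If function starts at final restoration (Month 3), one year of function is 3 + 12 = Month 15, where no visit is scheduled. Five years is 3 + 60 = Month 63, after the last visit. The two five-year figures may therefore be different quantities.

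**The case against.** The strongest reply is that the plan already points to an answer. A duration parameter is addressed directly by a curve comparison, sizing rests on five-year survival, and the landmark rates could be read as supportive. This stands in part. But the sizing sentence names no test, and it fits a five-year proportion at least as well as a log-rank test. Nothing labels the other comparisons supportive. The paragraph does open with secondary parameters, yet the sentence at issue concerns implant survival curves.

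The second reply is that the inflation depends on the form of chi-square. This stands: with few failures, a continuity-corrected or exact form largely removes it. The plan does not specify the form, and its remark on exact methods concerns associations with other variables, so it does not settle the point. The corrected and exact ranges were computed only for 5% and 10% failure; with more failures the forms converge.

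A reader might also infer three things that the documents do not support:

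- That the 1-, 2- and 5-year list adds further tests. Those fractions are only to be evaluated.
- That 0.05 is plainly stated for survival. It is carried over from a misprinted sentence about adverse events.
- That one or two early failures generally produce significance. This holds only for the uncorrected test at 160 v 40.

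**Conclusion.** The gap is real: the primary parameter has several between-arm comparisons and none is named as decisive. If any significant result at an inferred two-sided 0.05 were taken as a survival difference, the false-positive rate with independent implants would be roughly 5–14% with uncorrected chi-square and about 4–7% with a corrected or exact form, against about 3–6% for one pre-named test. It is lowest when most failures are early.

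A reader might infer that the error rate is simply doubled. About 9–10% is a fair middle value for the uncorrected test across the wider assumptions, but the documents fix neither failure rate, timing nor the form of chi-square, so no single multiple belongs to the plan.

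Clustering of implants within patients is a separate problem. With two implants per patient, 5% failure and an assumed intra-patient correlation of 0.2–0.5, the any-test rate was about 10–14%, and log-rank alone ran at 5.1–10.1%. Naming one test does not cure that.

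**What to change.** In the Statistical Analyses section:

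- Name one decisive survival comparison and state its level. For example: the log-rank test of time from placement to implant failure through Month 60, at two-sided 0.05, which is consistent with the five-year sizing. A five-year proportion would also fit the sizing; what matters is that one is chosen in advance.
- Remove the open choice of Wilcoxon, or label it a sensitivity analysis. This is for clarity; it changes the error rate very little.
- Use one landmark list and one clock throughout, and say whether time runs from placement or from restoration.
- Report the landmark survival fractions as descriptive estimates with 95% confidence intervals, without significance claims. If the three chi-squares were instead kept as joint decisions, each would need a level of about 0.019–0.031 to hold 5% overall, depending on failure timing.

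The cost is wording only: no more patients, visits or data. The downside is small: a difference seen only at six months or one year could not be claimed as significant on its own.

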A global evaluation of the status of the area where the study implants were placed will be recorded using gingival and plaque indices. The **gingival index** will be ranked as follows: (0) Normal gingiva; (1) Mild inflammation, slight change in color, slight edema, no bleeding on probing; (2) Moderate inflammation, redness, edema and glazing, bleeding on probing; (3) Severe inflammation, marked redness and edema, ulcerations; tendency toward spontaneous bleeding.

The criteria for **plaque index** are as follows: (1) No plaque in gingival area; (2) No plaque visible by the unaided eye, but plaque is made visible on the point of the probe after it has been removed across surface at entrance of gingival crevice; (3) Marginal area is covered with a thin to moderately thick layer of plaque; deposit is visible to the naked eye; (4) Heavy accumulation of soft matter, the thickness of which fills out a niche produced by gingival margin and tooth surface; interdental area is stuffed with soft debris.

EVALUATION CRITERIA

Implant Integration Success

An implant will be considered successful if it is immobile at specific points in time. Additionally, long-term implant success will be achieved when tested with instrument pressure at follow-up evaluations with no evidence of persistent peri-implant radiolucency, no persistent or irreversible signs and symptoms of pain, infection, neuropathies, or paresthesia.

Additionally the correlation of initial stability (as reflected in the Insertion Torque Profile) and clinical success will be assessed. The individual implant will be considered the experimental unit. The Insertion Torque Profiles for failed implants will be compared with those from successful implant cases to determine if this baseline variable is predictive.

Radiological Crestal Bone Level Changes

Bone levels measured at three and six month, and all follow-up intervals from both treatment groups will be compared to those measurements observed at the time of implant placement surgery to derive *changes from baseline* values. Differences between groups will be calculated and used to determine if the crestal bone changes are different between groups. A difference of 5% will be considered relevant.

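### The six-month crestal bone verdicts of equivalence and superiority rest on the test arm's mean against an assumed 0.75 mm, not on the test-minus-control difference

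*Combined protocol and SAP*

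**What the plan says.** The Statistical Analyses section frames crestal bone as a comparison of two implants, namely "equivalence in the changes in alveolar crestal bone between the modified implant (T3) and its predecessor". It reports that six-month means in earlier studies of the sponsor's implants "have ranged from a mean of 0.37 mm to 1.2 mm at the six month (Visit 6) time point", and from there makes an "assumption that the control implant will have a change-from-baseline mean value of 0.75 mm at the 6 month (Visit 6) time period".

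The verdicts follow directly. The condition for equivalence is this: "To declare equivalence the Test implant system will need to have a crestal bone change-from-baseline mean bone level regression of 0.75 ± 0.15 mm". The stronger claim has its own cut-off, given as "or to declare superiority a mean value of 0.55 mm or lower". Both are conditions on the test arm's mean.

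The same section also plans a comparison of the arms: "At each time point the treatment groups will be compared using the analysis of variance or the blocked Wilcoxon test, as appropriate". Under Evaluation Criteria, Radiological Crestal Bone Level Changes, group differences are to be calculated, and "A difference of 5% will be considered relevant". Neither statement gives an equivalence margin, and neither is linked to the two verdicts.

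The Patient Sample and Randomization sections give 100 patients, randomised as patients in an 80:20 ratio, each receiving one implant type and contributing at least two implants. Study Design adds matched control cases from other trials to bring the groups to 1:1. The sample size is said to rest on five-year survival. No SD is given for crestal bone change.

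**The concern.** The question is about a difference between two implants, but the rule that answers it contains only one of them. The randomised control arm is there to show how much bone the predecessor loses in these centres, with these surgeons and this radiographic method. If the control mean is not 0.75 mm, the rule can give the wrong verdict in either direction, and the observed control data cannot correct it.

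The rule also treats a sample mean as if it were known exactly. A standard equivalence test accepts a product lying exactly at the margin at most 5% of the time; a rule on the point estimate has no such limit. At stake is the crestal bone claim named in the study title.

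**Working it through.** **The plan's own thresholds.** 0.75 − 0.15 = 0.60 mm and 0.75 + 0.15 = 0.90 mm, so equivalence means a test mean of 0.60 to 0.90 mm. The superiority cut lies 0.75 − 0.55 = 0.20 mm below the assumed control mean. There is no power or SD figure for crestal bone to reproduce.

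**Step 1: what the fixed thresholds mean as differences.** Subtract a control mean C from each threshold. The values 0.37 and 1.2 are the ends of the range the protocol cites; 0.50 is an intermediate illustration. Positive differences mean that the test implant loses more bone.

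| C (mm) | Test − control over the equivalence band | Test − control at the superiority cut |
|---|---|---|
| 0.37 | +0.23 to +0.53 | +0.18 |
| 0.50 | +0.10 to +0.40 | +0.05 |
| 0.75 | −0.15 to +0.15 | −0.20 |
| 1.2 | −0.60 to −0.30 | −0.65 |

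Only the 0.75 row is a ±0.15 mm equivalence rule. A worse test implant can be called superior whenever C is below 0.55 mm. In the other direction, with C = 1.2 mm a test mean of 0.75 mm is called only equivalent, although 0.75 − 1.2 = −0.45 mm, a clear benefit. This step needs no SD.

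**Step 2: chance of each verdict.** Take n = 80 test patients (80% of 100), a true test mean m, and SE = SD/√80. The SD of patient-level change is assumed to be 0.4 to 1.0 mm.

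- Equivalence: P = Φ((0.90 − m)/SE) − Φ((0.60 − m)/SE). At m = 0.90 this is 0.5 − Φ(−0.30/SE), which is 50% at SD 0.4 (SE 0.045) and 49.6% at SD 1.0 (SE 0.112).
- Superiority: P = Φ((0.55 − m)/SE). At m = 0.50 this is Φ(1.12) = 87% at SD 0.4 and Φ(0.45) = 67% at SD 1.0. These chances are the same whatever the control arm does, including a control mean of 0.37 mm.

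**Step 3: what a between-arm rule could deliver.** Let d be test minus control. With 80 versus 20 patients, SE(d) = SD × √(1/80 + 1/20) = 0.25 × SD, and the 90% CI half-width is 1.645 × SE(d). Equivalence power at d = 0 is 2Φ(0.15/SE(d) − 1.645) − 1, or zero if that is negative.

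| Assumed SD (mm) | SE(d) | 90% half-width | Equivalence power at d = 0 |
|---|---|---|---|
| 0.3 | 0.075 | 0.12 | 28% |
| 0.5 | 0.125 | 0.21 | 0 |
| 0.7 | 0.175 | 0.29 | 0 |

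The half-width reaches the margin when SD = 0.15/(1.645 × 0.25) = 0.36 mm. Above that, no result can satisfy the rule. Treating 160 versus 40 implants as independent, which is optimistic, gives 37% at SD 0.4 and zero at SD 0.6 or more.

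**The case against.** **The arms are compared.** A reader might infer that the randomised control plays no part in the crestal bone analysis. The documents do not support that: a between-group test is planned at every visit and group differences are calculated. What stands is narrower. That test looks for a difference, has no equivalence margin and is not tied to either verdict, and a non-significant result would not show equivalence.

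**The band may only illustrate a margin.** Perhaps 0.75 ± 0.15 mm is shorthand for a ±0.15 mm margin around the control. But the text gives it as the condition for declaring and offers no rule on a difference. If a margin was meant, saying so is the repair.

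**The 0.37 mm control mean is hypothetical.** This is fair. The cited range comes from earlier studies of the sponsor's implants, not specifically of the control implant; two of the three cited titles concern expanded-platform or Prevail implants, and the protocol does not say which study gave which mean. Nothing shows that the control will lose so little bone.

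**Crestal bone is secondary.** Statistical Analyses calls it so, but Study Design names it in the primary endpoint and the null hypothesis covers it. Its status does not excuse a rule that answers another question.

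**Test means of 0.55 to 0.60 mm get no verdict.** A reader might call this a defect in itself. It is minor: any scheme with two claims leaves results that earn neither.

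**Conclusion.** The point holds for the declaration rule. As written, equivalence and superiority are judged on the test arm's point estimate against a planning assumption, and the verdict is right as a between-implant statement only if the control mean is 0.75 mm. Across the range the protocol cites, the same rule can call a test implant superior while up to 0.18 mm worse, or only equivalent while 0.45 mm better. Those are arithmetic scenarios, not predictions. The roughly 50% chance of declaring equivalence at a true test mean of 0.90 mm holds for all assumed SDs from 0.4 to 1.0 mm with 80 test patients.

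A reader might also infer that the 5% under Evaluation Criteria contradicts the 0.15 mm band by a factor of four. That needs a base the protocol does not give. If 5% means 5% of 0.75 mm, it is 0.0375 mm, against 0.15/0.75 = 20%; otherwise the size of the mismatch is unknown. The two statements need reconciling, and nothing in the documents settles which should give way.

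**What to change.** Replace the two declaration sentences in Statistical Analyses along these lines:

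- Let d be the mean change at Visit 6 in the test arm minus that in the concurrent randomised control arm, estimated with a model that allows for several implants per patient, for example a random patient effect. Patients are randomised, although the plan currently treats the implant as the experimental unit.
- Declare equivalence if the 90% CI for d lies within −0.15 to +0.15 mm.
- Declare superiority if the two-sided 95% CI for d lies below 0 and the estimate is −0.20 mm or lower. This keeps the benefit implied by 0.75 versus 0.55 mm.
- Use the matched external controls only in an analysis labelled as supportive.
- State the base of the 5% under Evaluation Criteria and reconcile it with the 0.15 mm margin.

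The wording is a small change; the consequence is not. The plan should state an expected SD and the precision it implies. With 80 versus 20 patients, equivalence power is about 28% at SD 0.3 mm and zero above about 0.36 mm. For 80% power at d = 0 with equal arms, n per arm = 2 × SD² × (1.645 + 1.282)²/0.15², which is 122 at SD 0.4 and 275 at SD 0.6. Adding external controls to reach 80 versus 80 would cut the 90% half-width to 0.08, 0.13 or 0.18 mm at SD 0.3, 0.5 or 0.7 (1.645 × SD × √(2/80)), but that contrast is no longer wholly randomised. The superiority rule is also demanding: because the estimate must reach −0.20 mm, its power is at most 50% when the true difference is −0.20 mm.

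Unless the sample size changes, the plan should say that the randomised comparison may be unable to support an equivalence claim, and commit to reporting d with its confidence interval whatever the verdict.

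### A test mean crestal bone loss strictly between 0.55 and 0.60 mm earns neither declaration, although larger losses are declared equivalent

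*Combined protocol and SAP*

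**What the plan says.** The rule stands in the Statistical Analyses section, which introduces the topic so: "A secondary outcome question of this study is the equivalence in the changes in alveolar crestal bone". The control implant is assumed to have a "change-from-baseline mean value of 0.75 mm at the 6 month (Visit 6) time period". Two declarations are then defined, each by where the test mean falls. For equivalence the test implant needs a mean "bone level regression of 0.75 ± 0.15 mm; or to declare superiority a mean value of 0.55 mm or lower".

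Neither condition mentions a confidence interval, a standard error or the observed control mean. The same paragraph also plans a test: "At each time point the treatment groups will be compared using the analysis of variance or the blocked Wilcoxon test, as appropriate". It does not say how that test bears on either label. The only other criterion for crestal bone is under Evaluation Criteria, Radiological Crestal Bone Level Changes: "A difference of 5% will be considered relevant".

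**The concern.** The two declarations do not meet. The equivalence band stops at 0.60 mm and superiority starts at 0.55 mm, and nothing in the document assigns a label to the interval between them. The order of verdicts is therefore broken. As mean bone loss rises, the label goes from superior to none, then to equivalent, then to none again.

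The study title names preservation of crestal bone as a purpose of the trial. A rule under which a test mean of 0.57 mm earns nothing while 0.85 mm earns equivalence works against that purpose. The gap also lies where a modest benefit over the assumed control would fall. If the result landed there, the sponsor would have to choose a label after seeing the data.

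**Working it through.** **Limits from the plan's own figures.**

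- Lower equivalence limit: 0.75 − 0.15 = 0.60 mm.
- Upper equivalence limit: 0.75 + 0.15 = 0.90 mm.
- Superiority: 0.55 mm or lower, that is 0.75 − 0.55 = 0.20 mm below the assumed control.
- Gap: 0.60 − 0.55 = 0.05 mm wide. Both ends are excluded, since 0.55 is superior and 0.60 is equivalent.

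**Labels under the rule as written.**

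| Test mean (mm) | Against 0.75 mm | Label |
|---|---|---|
| 0.50 | 0.25 less | superior |
| 0.55 | 0.20 less | superior |
| 0.57 | 0.18 less (24%) | none |
| 0.60 | 0.15 less | equivalent |
| 0.85 | 0.10 more (13%) | equivalent |
| 0.90 | 0.15 more | equivalent |
| 0.95 | 0.20 more (27%) | none |

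The 5% criterion does not fill the gap. Read as 5% of 0.75 mm it is 0.0375 mm. A mean of 0.57 mm exceeds that difference and still gets no label.

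**Chance that the observed mean falls in the gap.** The Patient Sample section gives 100 patients and the Randomization section an 80:20 split, so 80 test patients. The documents give no SD for bone change, so 0.5, 0.75 and 1.0 mm are assumed, with one mean per patient. For a true test mean μ and SE = SD/√80:

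P(gap) = Φ((0.60 − μ)/SE) − Φ((0.55 − μ)/SE)

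The SEs are 0.0559, 0.0839 and 0.1118 mm. For example, with μ = 0.575 and SD 0.5: Φ(0.447) − Φ(−0.447) = 0.673 − 0.327 = 0.345.

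| True test mean (mm) | SD 0.5 | SD 0.75 | SD 1.0 |
|---|---|---|---|
| 0.55 | 31% | 22% | 17% |
| 0.575 | 35% | 23% | 18% |
| 0.60 | 31% | 22% | 17% |
| 0.65 | 15% | 16% | 14% |
| 0.75 | 0.4% | 2.8% | 5.3% |

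The plan treats implants as the experimental units. With 160 test implants (two per patient), taken as independent and with SD 0.5, the chances are 47% at 0.575 mm, 40% at 0.60 mm, 10% at 0.65 mm and under 0.1% at 0.75 mm. Correlation within patients would move these figures back towards the table.

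**What a confidence-limit rule would do instead.** Suppose T3 were called no worse when the upper limit of a two-sided 95% interval for test minus control lies below +0.15 mm. If the implants are truly equal, the chance of that declaration is Φ(0.15/SE − 1.96).

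- With 80 test and 20 control patients, SE = SD × √(1/80 + 1/20) = 0.25 × SD, that is 0.125, 0.1875 and 0.25 mm. The chance is Φ(−0.76) = 22%, Φ(−1.16) = 12% and Φ(−1.36) = 9%.
- With 80 controls, using the extra matched cases foreseen in the Study Design section, SE = 0.158 × SD. The chance is 48%, 24% and 16%.

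**The case against.** A reader might infer that a mean in the gap leaves the bone question with no permitted conclusion, or that it counts as a failure. The documents do not say that. The estimate and the analysis of variance or blocked Wilcoxon comparison would still be reported, and the plan nowhere calls the gap a failure. This narrows the point but does not remove it, because the test is not linked to either label.

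It can also be said that any two-sided equivalence rule excludes results that are too good as well as too bad, and that asking for a larger difference before claiming superiority may be deliberate. Both remarks are fair, and the text does not settle what was intended. But this plan offers superiority as the verdict beyond the favourable side of the band, and then starts it 0.05 mm further on without saying what applies in between.

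A zone with no label is ordinary when a rule uses confidence intervals, because it then reflects imprecision. Here the rule uses the mean alone, so a mean of 0.57 mm would stay unlabelled however precisely it was estimated. Reading ± 0.15 as an SD does not help either. The sentence sets a condition on a mean, and under that reading no equivalence range would exist.

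Finally, the Statistical Analyses section calls the question secondary and bases the sample size on five-year survival. That limits the weight of the point, although the Study Design section names crestal bone regression as part of the primary endpoint.

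**Conclusion.** The decision rule is defective as written: means strictly between 0.55 and 0.60 mm have no declaration, while means showing more bone loss, from 0.60 to 0.90 mm, are declared equivalent. This follows from the plan's own figures and needs no assumption.

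How much it matters depends on the unknown true mean and on SDs that the plan does not give. With 80 test patients and SDs of 0.5 to 1.0 mm, the gap would be hit about 14% to 35% of the time if the true test mean is about 0.55 to 0.65 mm. At the plan's reference value of 0.75 mm the chance is 0.4% to 5%, so the larger figures should not be read as the general risk. The plan cites earlier six-month means from 0.37 to 1.2 mm, so a true mean near the gap is possible, but nothing in the documents makes it the expected case.

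**What to change.** Before data are seen, reword the rule so that the verdicts are ordered and meet. One way that keeps the existing figures:

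- Declare T3 no worse (at least equivalent) for any mean up to 0.90 mm.
- In addition, declare it superior at 0.55 mm or lower.

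A mean of 0.57 mm would then be no worse, 0.95 mm would still earn nothing, and less bone loss could never bring a lesser verdict. The paragraph should also say how the between-group test relates to these labels.

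The wording takes a sentence or two. The real cost is that the lower equivalence limit is dropped, so the claim becomes at least equivalent and not two-sided equivalence, which is the question the plan now states. This change closes the gap only. The rule would still rest on the mean alone and on an assumed control value.

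If the sponsor prefers a confidence-limit rule against control, it should define the comparator (randomised controls only, or with the added matched cases) and state whether the limit is one- or two-sided. It should also state the price: under the 80:20 split, with a two-sided 95% limit and the SDs assumed above, T3 would be declared no worse only about 9% to 22% of the time when the implants are truly equal.
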